#### **10.1.1.4 Preexisting Medical Conditions (Baseline Conditions)**

A preexisting medical condition should be recorded as an AE or SAE only if the frequency, severity, or character of the condition worsens during the study. When recording such events on an Adverse Event CRF, it is important to convey the concept that the preexisting condition has changed by including applicable descriptors (e.g., “more frequent headaches”).

#### **10.1.1.5 Vital Signs, ECG and Physical Examination Results**

Changes in vital signs, ECG and physical examination test results will be recorded as an AE in the CRF, if they are judged clinically relevant by the investigator.

### **10.2 Adverse Events of Special Interests (AESI)**

The following events are considered as Protocol-specified events of special interests:

- **Any gastrointestinal and non-gastrointestinal perforation, leakage, fistula formation, or abscess.**

In such cases the following additional information will need to be collected, documented in the respective comment field of the CRF page and the respective narratives of the SAE, and be forwarded to Boehringer Ingelheim:

- Location of perforation, leakage, fistula, abscess
- Location/extent of abdominal tumor manifestations
- Imaging & reports (CT, ultrasound, endoscopy, pathology, etc.)
- Prior surgery (location, wound healing complications)
- Concomitant diseases with GI involvement (e.g., M Crohn, vasculitis, tuberculosis, diverticulitis)

- Thromboembolic events (or predisposition)
- **Drug-induced liver injury.**

Drug-induced liver injury is under constant surveillance by sponsors and regulators and is considered a protocol-specified adverse event of special interest (AESI). Timely detection, evaluation, and follow-up of laboratory alterations of selected liver laboratory parameters to distinguish an effect of the investigational drug from other causes are important for patient safety and for the medical and scientific interpretation of the finding.

The following are considered as protocol-specified AESI:

- An elevation of ALT and / or AST > 5x ULN without bilirubin elevation measured in the same blood draw sample
- An elevation of AST and/or ALT > 2.5 fold ULN combined with an elevation of bilirubin to > 1.5 fold ULN measured in the same blood draw sample

Patients showing the above laboratory abnormalities need to be followed up until the protocol specific retreatment criteria have been met and according to **Appendix C** [Boehringer Ingelheim: *Procedures for the follow-up of drug-induced liver injury (DILI)*].

Protocol-specified AESI are to be reported to Boehringer Ingelheim an expedited manner similar to Serious Adverse Events (**Section 10.4**), even if they do not meet any of the seriousness criteria.

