## 5 PARTICIPANT SELECTION

### 5.1 Inclusion Criteria

To be included in this study, participants must meet the following criteria:

1. Age  $\geq$  18 years of age.
2. Have an ECOG Performance Status of 0 – 1. Refer to **Appendix B**.
3. Have the following clinical laboratory values:
  - Hemoglobin  $\geq$  9 g/ dL
  - Absolute neutrophil count  $\geq$  1500/ mm^3
  - Platelet count  $\geq$  100,000/ mm^3
  - Creatinine  $\leq$  1.5 ULN AND CrCl  $>$  50 mL/min by Cockcroft-Gault equation:
    - Males =  $(140 - \text{age [yrs]})(\text{Body weight [kg]})(72)(\text{serum creatinine [mg/dL]})$
    - Females =  $0.85 * (140 - \text{age [yrs]})(\text{Body weight [kg]})(72)(\text{serum creatinine [mg/dL]})$
  - Bilirubin  $\leq$  ULN
  - AST / ALT  $\leq$  1.5 ULN if without liver metastases
  - AST/ ALT  $\leq$  2.5 x ULN if with liver metastases
  - Coagulation parameters: International normalized ratio (INR)  $\leq$  2, prothrombin time (PT) and partial thromboplastin time (PTT)  $<$  1.5 X institutional ULN
4. Have measurable disease per RECIST 1.1 criteria.
5. Histologically or cytologically proven adenocarcinoma of the colon or rectum.
6. Prior progression following a fluoropyrimidine-based therapy and progression following or intolerance to irinotecan and oxaliplatin, as well as anti-EGFR therapy (e.g., panitumumab or cetuximab) for RAS wild-type patients.
7. Ability to swallow and retain oral medication.
8. Participants of child-bearing potential must agree to use adequate contraceptive methods (e.g., hormonal or barrier method of birth control; abstinence) prior to study entry and for three months following completion of therapy. Should a woman become pregnant or suspect she is pregnant while she or her partner is participating in this study, she should inform her treating physician immediately.
9. Participant or legal representative must understand the investigational nature of this study and sign an Independent Ethics Committee/Institutional Review Board approved written informed consent form prior to receiving any study related procedure.

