### 6.4 Definition of Dose-Limiting Toxicity

Dose limiting toxicity will be defined as any event which meets the criteria below and occurs within the 1st cycle of therapy (21 days).

The following drug-related adverse events will qualify as DLT if considered drug-related:

- Non-hematologic toxicity ≥ Grade 3 (CTCAE v4) **except:** transient electrolyte abnormality, alopecia, sub-optimally treated nausea, vomiting or diarrhea, and isolated elevation of gamma glutamyl transpeptidase. In particular,
  - Gastrointestinal toxicity (e.g. nausea, vomiting, diarrhoea, abdominal pain) or hypertension ≥ CTCAE Grade 3 despite optimal supportive care/ intervention.
  - Nintedanib (BIBF1120) related liver toxicity except GGT\*\*\* as specified below:
    - AST/ALT > 5x ULN\* independent of bilirubin
    - AST/ALT > 2.5 x ULN\*\* **together with** total bilirubin > 1.5 ULN\*\*

\* corresponding to CTCAE Grade 3 toxicity

\*\* corresponding to CTCAE Grade 2 toxicity

\*\*\* An isolated GGT elevation with no corresponding ALT/AST increase will not be considered as DLT.

- Hematological toxicity
  - CTCAE Grade 4 neutropenia that is uncomplicated (not associated with fever  $\geq 38.5^{\circ}\text{C}$ ) only if continuing for  $> 7$  days
  - CTCAE Grade 4 febrile neutropenia of any duration if associated with fever  $\geq 38.5^{\circ}\text{C}$
  - Platelet decrease to CTCAE Grade 4, or decrease to CTCAE Grade 3 associated with bleeding or requiring transfusions
- Inability to resume nintedanib (BIBF1120) dosing within 14 days of stopping due to treatment related toxicity
- In case adverse events with CTCAE Grade 3/4 were not judged as DLT from a clinical point of view, the Principle Investigator will obtain a confirmation from the individual investigator regarding the appropriateness of the judgment

Dose escalation will proceed within each cohort according to the scheme in **Table 3**.

Participants who do not have a DLT and who do not complete a full cycle of treatment (at least 75% of the prescribed dose of both nintedanib and capecitabine) will be replaced in the study.

Management and dose modifications associated with the above AEs are outlined in **Section 6.5** and **Section 6.5.2**.

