#### **10.4 Investigator Reporting: Notifying Boehringer Ingelheim (BI) and NCCN**

The principle investigator at each respective site will report all SAEs and non-serious AEs which are relevant to a reported SAEs and AESIs by fax using a MEDWATCH 3500A form with the completed BI FAX Cover Sheet to BI Unique Entry Point and NCCN, as detailed below in accordance with the following timelines:

- **Within 5 calendar days** upon receipt of initial and follow-up SAEs containing at least one fatal or immediately life-threatening event.
- **Within 10 calendar days** upon receipt of any other initial and follow-up SAEs.

Boehringer Ingelheim Pharmaceuticals, Inc.  
[name]  
[name]  
[contact]

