**Within 15 Calendar Days**

Any adverse event that meets **ALL** the following criteria:

- Related or possibly related to the use of the study drug;
- Unexpected; and
- Serious but not fatal or life-threatening;

Or, meets **ANY** of the following criteria:

- A previous adverse event that is not initially deemed reportable but is later found to fit the criteria for reporting (report within 15 days from when event was deemed reportable).
- Any findings from other studies, including epidemiological studies, pooled analysis of multiple studies, or other clinical studies conducted with the study drug that suggest a significant risk in humans exposed to the drug.
- Any findings from animal or in vitro testing that suggest a significant risk for human participants including reports of mutagenicity, teratogenicity, or carcinogenicity or reports of significant organ toxicity at or near the expected human exposure.
- Any clinically important increase in the rate of occurrence of a serious, related or possibly related adverse event over that listed in the protocol or investigator brochure.

Sponsors are also required to identify in IND safety reports, all previous reports concerning similar adverse events and to analyze the significance of the current event in the light of the previous reports.

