#### Introduction

##### *Drug-induced liver injury*

Drug-induced liver injury (DILI) has been the most frequent single cause of safety-related drug marketing withdrawals for the past 50 years (e.g., iproniazid), continuing to the present (e.g., ticrynafen, benoxaprofen, bromfenac, troglitazone, nefazodone). Accordingly, detection of drug-induced liver injury of an investigational compound has become an important aspect of patient's safety guarding in drug development.

The US-FDA has published a Guidance for Industry entitled, "Drug-Induced Liver Injury: Premarketing Clinical Evaluation"

(<http://www.fda.gov/downloads/Drugs/.../Guidances/UCM174090.pdf>) which outlines the detection, evaluation, follow-up and reporting of drug-induced liver injury in clinical trials. Drugs that have the potential for inducing severe liver injury may be identified by marked peak aminotransferase elevations (10x-, 15xULN), or the combination of hepatocellular injury (aminotransferase elevation  $\geq 3xULN$ ) and altered liver function (hyperbilirubinemia  $\geq 2xULN$ ) which is defined as potential "Hy's law case" if not explained by other causes including evidence of biliary obstruction (i.e., significant elevation of alkaline phosphatase, ALP,  $>2X$  ULN) or some other explanation of the injury (e.g., viral hepatitis, alcohol hepatitis, concomitant use of other known hepatotoxic drugs). This constellation predicts a poor outcome and although very rare, these potential cases have to be well characterized as soon as being identified as other confounding conditions may be the cause.

In further consideration of this FDA Guidance, any potential "Hy's Law case" has to be reported in an expedited manner to the FDA (i.e., even before all other possible causes of liver injury have been excluded) and be followed-up appropriately. The follow-up includes a detailed clinical evaluation and identification of possible alternative etiologies for the "Hy's Law case" constellation such as concomitant diseases (e.g. Hepatitis B) and/or other concomitant therapies that might potentially be hepatotoxic.

Although rare, a potential for drug-induced liver injury is under constant surveillance by sponsors and regulators. Therefore, this study requires timely detection, evaluation, and follow-up of laboratory alterations of selected liver laboratory parameters to ensure patients' safety.

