## Definition

The following changes in the laboratory values are considered to be a protocol-specific significant adverse event for all patients with normal values for ALT/AST at baseline:

- an elevation of ALT and / or AST > 5x ULN without bilirubin elevation measured in the same blood draw sample
- an elevation of AST and/or ALT >2.5 fold ULN combined with an elevation of bilirubin to >1.5 fold ULN measured in the same blood draw sample

These definitions are in line with the current dose reduction recommendations as outlined in all study protocols for BIBF 1120.

Patients showing these laboratory abnormalities need to be followed up until the protocol specific retreatment criteria have been met.

For patients with elevated ALT/AST values at baseline special considerations apply, if they are eligible for inclusion into the trial, e.g. if liver metastasis are present and do not qualify as exclusion criterion. For those special cases the BI contact person should be involved.

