## Procedures

1. Protocol-specified significant events are to be reported in an expedited manner similar as Serious Adverse Events, even if they do not meet any of the seriousness criteria and documented in the eCRF.
2. Replication of the following laboratory tests for confirmation within 48 hours:
  - AST, ALT
  - Bilirubin measurement (total and direct bilirubin)
  - Alkaline Phosphatase
  - Haptoglobin
  - Complete blood count and cell morphology
  - Reticulocyte count
  - CK
  - LDH

The results of these repeated laboratory tests must be documented on the eCRF /CRF forms and reported immediately via the SAE form to BI.

The investigator will report all SAEs and non-serious AEs which are relevant to reported SAEs and AESIs by fax using BI IIS SAE form or MedWatch 3500A form, and completed BI SAE Fax Cover sheet to BI Unique Entry Point as detailed below:

Boehringer Ingelheim Pharmaceuticals, Inc.  
[name]  
[name]  
[contact]

3. An evaluation of the patient within 48 hours with respect to but not limited to:
  - Abdominal ultrasound or clinically appropriate other imaging and investigations adequate to rule out biliary tract, pancreatic, intra- or extrahepatic pathology, e.g. bile duct stones, neoplasm, hepatic tumour involvement, biliary tract, pancreatic or intrahepatic pathology, vascular hepatic conditions such as portal vein thrombosis or right heart failure. These data need to be collected, documented in the respective field of the eCRF / CRF / additional documentation form, and the respective SAE form has to be updated and forwarded to BI.
  - Detailed history of current symptoms and concurrent diagnoses and medical history.
  - Detailed history of concomitant drug use (including non-prescription medications, herbal and dietary supplement preparations and e.g., steroids as concomitant supportive treatment), alcohol use, recreational drug use, and special diets detailed history of exposure to environmental chemical agents.
  - In case that both imaging and laboratory value did not unequivocally confirm cholestasis as the reason of ALT / AST increase, in particular if AP < 2x ULN, then please complete the following laboratory tests:
    - Clinical chemistry:
      - Alkaline phosphatase, cholinesterase (either plasma or red blood cell), albumin, PT or INR, CK, CK-MB, coeruloplasmin\*,  $\alpha$ -1 antitrypsin\*, transferrin, ferritin, amylase\*, lipase\*, fasting glucose\*, cholesterol, triglycerides
    - Serology:

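### Read literally, the liver AESI definition omits ALT/AST above 5x ULN with bilirubin above 1 and up to 1.5x ULN, and section 10.7 has no trigger that ensures FDA reporting of every potential Hy's Law case

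*Combined protocol and SAP*

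**What the plan says.** Section 10.2 names drug-induced liver injury as an AESI and gives two laboratory criteria, both judged within one blood sample. Limb 1 is "An elevation of ALT and / or AST > 5x ULN without bilirubin elevation measured in the same blood draw sample". Limb 2 is ALT/AST above 2.5x ULN together with bilirubin above 1.5x ULN. AESIs go to the drug supplier on an expedited basis even when not serious, and patients are followed under Appendix C.

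Appendix C repeats both limbs but says they are "considered to be a protocol-specific significant adverse event for all patients with normal values for ALT/AST at baseline". For patients with raised baseline values it promises individual handling with the supplier's contact and gives no criteria. Section 5.1 admits ALT/AST up to 1.5x ULN without liver metastases and up to "2.5 x ULN if with liver metastases".

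The liver DLT rule in section 6.4 uses AST/ALT above 5x ULN "independent of bilirubin", or above 2.5x ULN with bilirubin above 1.5x ULN. Tables 4 and 9 also attach no bilirubin condition to the 5x threshold.

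The introduction to Appendix C describes a potential Hy's Law case as aminotransferase at least 3x ULN with bilirubin at least 2x ULN and no other explanation. It says that any such case "has to be reported in an expedited manner to the FDA", before alternative causes have been ruled out. Section 10.7 lists what goes to the FDA when the sponsor holds the IND. A single event must be related or possibly related, unexpected, and either fatal or life-threatening (7 days) or "Serious but not fatal or life-threatening" (15 days).

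**The concern.** Limb 1 switches off once bilirubin is raised, and limb 2 switches on only above 1.5x ULN. Between the two, a patient whose ALT/AST alone would qualify loses AESI status because bilirubin has also risen. AESI status brings expedited reporting to the supplier, and repeat laboratory tests and an evaluation, each within 48 hours (Appendix C, Procedures). In Phase II, scheduled chemistry after the first day of treatment is drawn only on Day 1 of each 21-day cycle, so the AESI trigger is what calls for earlier repeat testing.

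On FDA reporting, Appendix C states a duty that covers every potential Hy's Law case. Section 10.7 is the list staff would work from, and it does not carry that duty. A case can satisfy Appendix C and still fail section 10.7 on causality, expectedness or seriousness, although Appendix C says not to wait for the question of cause to be settled.

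**Working it through.** No sample size or error rate is involved, so this is a check of logic. Let A be ALT or AST and B be total bilirubin, both as multiples of ULN.

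**Step 1. The rules as sets**

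- AESI (10.2, Appendix C), with elevation read as above ULN: {A > 5 and B ≤ 1} or {A > 2.5 and B > 1.5}.
- Liver DLT threshold (6.4): {A > 5} or {A > 2.5 and B > 1.5}.
- Liver interruption criteria (Table 4): {A > 5} or {A > 3 and B > 1.5}.
- Potential Hy's Law pattern (Appendix C): {A ≥ 3 and B ≥ 2}.

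**Step 2. Differences**

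The DLT set minus the AESI set is {A > 5 and 1 < B ≤ 1.5}. A grid of A from 2 to 12 and B from 0.8 to 3 found no other mismatch between these two rules. Table 4 minus the AESI set gives the same region.

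| A, B (x ULN) | 6.4 threshold | Table 4 liver criteria | Limb 1 | Limb 2 |
|---|---|---|---|---|
| 8, 1.0 | met | met | met | not met |
| 8, 1.2 | met | met | **not met** | **not met** |
| 8, 1.6 | met | met | not met | met |

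In the other direction, {2.5 < A ≤ 3 and B > 1.5} is an AESI but does not meet the liver criteria of Table 4 or 9. Appendix C's statement that its definitions agree with the dose-reduction recommendations is therefore not exact on either side.

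**Step 3. Effect of closing the gap**

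If limb 1 drops the bilirubin condition, the AESI set becomes {A > 5} or {A > 2.5 and B > 1.5}, which equals the 6.4 set. Defining elevation in limb 1 as B > 1.5 gives {A > 5 and B ≤ 1.5} or {A > 2.5 and B > 1.5}, which is the same set. Either wording leaves no 6.4-level event outside the AESI definition.

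**Step 4. Hy's Law cases and the AESI definition**

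A ≥ 3 implies A > 2.5, and B ≥ 2 implies B > 1.5. Every potential case therefore meets limb 2 and, under section 10.2, reaches the supplier. The open question is the FDA route.

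**Step 5. Hy's Law cases and section 10.7**

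Classify a case as related or not (2), unexpected or not (2), and non-serious, serious, or fatal/life-threatening (3): 2 × 2 × 3 = 12 profiles. The case-level criteria accept only related, unexpected cases that are serious or fatal/life-threatening: 1 × 1 × 2 = 2 profiles. These are logical combinations and say nothing about how often each occurs. The alternative triggers in section 10.7 (later reclassification, findings from other studies, animal or in vitro findings, a higher event rate) name neither Hy's Law nor AESIs. A case provisionally judged unlikely to be related, or judged non-serious, falls under Appendix C's duty but not under these criteria.

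**The case against.** **The gap depends on a reading.** Limb 1 gives no bilirubin threshold, and limb 2 speaks of elevation above 1.5x ULN. Carrying that meaning across closes the gap. No passage states this reading, however, and it fits poorly with the protocol's use of ULN itself as the bilirubin limit for entry (5.1), for starting a cycle (6.3) and for restarting (Table 5). Two sites could classify the same patient differently.

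**Other safeguards remain.** This stands. Table 4 interrupts both drugs, and DLT assessment applies in Phase I cycle 1. Section 6.4 equates 5x ULN with grade 3, and Tables 15 and 16 require grade 3 and 4 events to be reported whatever the attribution. Item 4 of the Appendix C procedures asks for at least weekly testing when enzymes and bilirubin are both raised, which arguably covers the gap.

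**The FDA duty is not lost.** This stands in part. Section 13.1 makes the appendices part of the protocol. A potential case can also qualify under 10.7 as possibly related, unexpected in severity (10.1.1) and an important medical event (10.3.1). A reader might infer that Hy's Law cases cannot meet 10.7; the documents do not support that. Nor do the enzyme elevations listed in 6.6.1 settle expectedness, which is judged against the investigator brochure, not provided here. What remains is a duty covering every case beside a list that need not capture every case.

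**Other inferences that do not hold**

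- That Appendix C leaves raised-baseline patients with no route: it gives them one, though without criteria.
- That the clocks conflict: repeat results must be "reported immediately via the SAE form to BI", while section 10.4 allows 10 calendar days "upon receipt of any other initial and follow-up SAEs". Prompt reporting satisfies both.
- That any first bilirubin rise on treatment enters the gap: ALT/AST must also exceed 5x ULN, and values between visits can skip the band.
- That planned AESI counts would be understated: section 12.4.1 tabulates toxicities by grade and plans no AESI count.

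**Conclusion.** The point holds as two wording defects in safety reporting. First, on the literal text, ALT/AST above 5x ULN with bilirubin above 1.0 and up to 1.5x ULN is at the DLT threshold and requires interruption, yet is not an AESI. What is lost is expedited AESI reporting and the 48-hour tests and evaluation. This assumes that elevation in limb 1 means above ULN. Second, Appendix C requires every potential Hy's Law case to go to the FDA, and section 10.7 has no matching item. This matters if the sponsor holds the IND, the condition on which 10.7 applies.

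A lesser inconsistency is that section 10.2 covers all patients, while Appendix C covers only those with normal baseline ALT/AST.

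The documents give no frequency for the gap pattern and no share of patients with raised baseline values, so the size in patients cannot be stated. The primary endpoint, sample size and planned toxicity tables are unaffected. The change is worth making because a DLT-level liver event should not depend on an undefined word for its reporting route.

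**What to change.** 1. In section 10.2 and Appendix C, reconcile limb 1 with section 6.4 so that every ALT/AST value above 5x ULN is an AESI for reporting purposes, for instance by replacing the bilirubin condition with "independent of bilirubin".
2. Add an item to section 10.7: a potential Hy's Law case as described in Appendix C is submitted for expedited FDA reporting regardless of seriousness, expectedness or final attribution. Cross-reference Appendix C there.
3. Reconcile the scope of section 10.2 with that of Appendix C, and state which criteria apply to patients with raised baseline ALT/AST. The choice of baseline rule is the sponsor's.
4. Reconcile or remove Appendix C's statement that its definitions match the dose-reduction recommendations. This review takes no position on which liver threshold is right for dose handling.

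The cost is a wording amendment with IRB approval under section 15.1 and a few more expedited reports. Items 1 to 3 need no change to any dose rule, visit schedule or planned analysis.
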